11.2.2 SAEs (Including Deaths) and Adverse Events Leading to Study Drug Discontinuation

Deaths and all SAEs will be presented in listing format. In addition, SAEs will be summarized by System Organ Class and MedDRA Preferred Term.

11.2.3 Safety Subgroup Analysis

The AE overview and AE by SOC and preferred term in each period will also be analyzed with respect to the actual values of:

- concomitant PsA at baseline (Yes: baseline total TJC and SJC counts ≥ 3 versus No: otherwise) among the subjects at the selected sites
- Dichotomous body weight (≤ 90 kg versus > 90 kg)
- Dichotomous body weight (\leq median versus $>$ median)

11.3 Analysis of Laboratory Data

For the assessments of laboratory data, values observed more than 105 days after the last dose of study drug will be excluded.

Listing and descriptive statistics of laboratory values over time, change from baseline, and extreme abnormal value on treatment will be provided. Extreme abnormal value is the value which is most significantly away from the reference range. Frequency of subjects with transitions relative to reference range and listing of subjects with significant abnormal laboratory values will be presented as well.

11.3.1 Variables and Criteria Defining Abnormality

Clinical laboratory tests performed by central laboratory service provider are listed below.

Table 11. Clinical Laboratory Tests

Category	Test Name
Haematology	Hematocrit (Hct) Hemoglobin (Hb) Glycosylated Hbc (HbA1c) White Blood Cells/Leukocytes Platelet Count/Thrombocytes
Diff. Automatic	Neutrophils (relative and absolute count) Eosinophils (relative and absolute count) Lymphocytes (relative and absolute count)
Enzymes	AST (GOT) ALT (GPT) Alkaline Phosphatase (AP) Creatine Kinase (CPK) Gamma-Glutamyl Transferase (GGT/γ-GT) Lactic Dehydrogenase (LDH) Amylase Lipase
Electrolytes	Calcium Sodium Potassium
Substrates	Glucose BUN Uric acid Creatinine eGFR (estimated by CKD-EPI formula) Bilirubin Total Albumin C-Reactive Protein (CRP) (high sensitivity) Cholesterol, total Triglycerides LDL-Cholesterol HDL-Cholesterol
Urinalysis (dipstick)	Urine Glucose

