5.3.3 Safety laboratory parameters

The laboratory tests listed in Table 5.3.3: 1 will be performed by the central laboratory service provider. A local laboratory may be used for selected tests in exceptional cases. Patients should be fasting for at least 8 hours prior to the blood sample being taken (except screening visit).

Instructions regarding sample collection, sample handling/processing, and sample shipping are provided in the Laboratory Manual in the ISF. For time points of laboratory sampling, see [Flow Chart](#).

Laboratory results (i.e., all safety laboratory and clinical laboratory data relevant for current clinical practice) of the patients will be available in real time to the respective investigator (via laboratory reports) and to the sponsor (via the central laboratory website) and selected abnormal laboratory alerts will be flagged to the site and sent to sponsor in real time.

Clinically relevant abnormal findings will be reported as baseline conditions or AE's. A clinically relevant value may be either in or outside the reference range. Clinically relevant abnormal laboratory test results must be confirmed using an unscheduled visit laboratory kit and should be repeated until normalisation or stabilisation or until an alternative explanation has been found. Abnormal laboratory values will be also graded for intensity by using RCTC Version 2.0 criteria ([R13-3515](#)).

Table 5.3.3: 1 Laboratory tests

Category	Test name
Haematology	Hematocrit Hemoglobin (Hb) Glycosylated Hbc (HbA1c) Red Blood Cell Count/Erythrocytes Reticulocyte Count White Blood Cells/Leukocytes Platelet Count/Thrombocytes
Differential Automatic	Neutrophils (relative and absolute count) Eosinophils (relative and absolute count) Basophils (relative and absolute count) Monocytes (relative and absolute count) Lymphocytes (relative and absolute count)

Table 5.3.3: 1 (continued)

Laboratory tests

Category	Test name
Differential Manual (if Differential Automatic is abnormal)	Neutrophils, bands (Stabs) Neutrophils, polymorphonuclear (PMN) Eosinophils Basophils Monocytes Lymphocytes
Coagulation	Activated Partial Thromboplastin Time (aPTT) Prothrombin time (INR) Fibrinogen
Enzymes	AST(GOT) ALT(GPT) Alkaline Phosphatase (AP) Creatine Kinase (CK) CK-MB, only if CK is elevated Gamma-Glutamyl Transferase (GGT/γ-GT) Lactic Dehydrogenase (LDH) Amylase Lipase
Electrolytes	Calcium Sodium Potassium Chloride Bicarbonate

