Substrates	Glucose BUN Uric acid Creatinine eGFR (estimated by CKD-EPI formula) Bilirubin Total Bilirubin Direct (if total is elevated) Bilirubin Indirect (if total is elevated) Troponin (reflex, in case of elevated CK) Albumin C-Reactive Protein (CRP) (high sensitivity) Cholesterol, total Triglycerides LDL-Cholesterol HDL-Cholesterol
Urine Pregnancy test (only for female patients of childbearing potential; test done in clinic)	Human Chorionic Gonadotropin in the urine
Serum Pregnancy test (only for female patients of childbearing potential at screening or if urine pregnancy test is positive)	Human Serum Chorionic Gonadotropin
Hormones (only at screening)	TSH, (free T3 and T4 in case of abnormal TSH)
Autoantibodies (only at screening)	Rheumatoid Factor

Table 5.3.3: 1 (continued)

Laboratory tests

Category	Test name
Urinalysis (dipstick)	Urine Nitrite Urine Protein Urine Glucose Urine Ketone Urobilinogen Urine Bilirubin Urine RBC/Erythrocytes Urine WBC/Leukocytes Urine pH
Urine-Sediment (microscopic examination, only if urine analysis abnormal)	Urine Sediment Bacteria Urine Cast in Sediment Urine Squamous Epithelial Cells Urine Sed. Crys., Unspecified Urine Sediment RBC/Erythrocytes Urine Sediment WBC/Leucocytes
Urine	Albumin (quantitative) Creatinine Albumin/creatinine ratio
Infection screening	Hepatitis B Surface Antigen (qualitative) ¹ Hepatitis B Surface Antibody (qualitative) ¹ Hepatitis B Core Antibodies total (qualitative) ¹ Hepatitis B Virus DNA (quantitative) ^{1,2} Hepatitis C Antibodies (qualitative) ¹ HIV-1, and HIV-2 Antibody (qualitative) ^{1,2} QuantiFERON®-TB ³ (if applicable)

¹ Hepatitis B, hepatitis C and HIV testing will be performed at screening and FU2/EOO Visit.

² If Hepatitis B Surface Antigen is negative but Hepatitis B Core Antibodies total is positive and/or Hepatitis B Surface Antibody is positive, Hepatitis B Virus DNA will be quantified. If HBV DNA level is undetectable (<20 IU/mL) at screening, the patient can participate in this trial. However, HBV DNA level will be monitored at least every 6 months.

³ TB testing will be performed at screening and FU2/EOO Visit. QuantiFERON®, T-SPOT® or PPD skin test may be performed. T-SPOT® and PPD skin test will be performed at local laboratory.

5.3.4 **Electrocardiogram**

The 12-lead ECGs will be performed as scheduled in the [Flow Chart](#).

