In case of clinical symptoms of hepatic injury (icterus, unexplained encephalopathy, unexplained coagulopathy, right upper quadrant abdominal pain, etc.) without lab results (ALT, AST, total bilirubin) available, the investigator should make sure these parameters are analysed, if necessary in an unscheduled blood test. Should the results meet the criteria of hepatic injury alert, the procedures described in the DILI checklist should be followed.

Intensity of AEs

The intensity grading of AEs will be performed according to Rheumatology Common Toxicity Criteria (RCTC) Version 2.0 developed by OMERACT ([R13-3515](#)). Refer to ISF for intensity/severity classification. Intensity options are:

Grade 1	mild
Grade 2	moderate
Grade 3	severe
Grade 4	life –threatening

Causal relationship of AEs

The definition of an adverse reaction implies at least a reasonable possibility of a causal relationship between a suspected medicinal product and an AE. An adverse reaction, in contrast to an AE, is characterised by the fact that a causal relationship between a medicinal product and an occurrence is suspected.

Medical judgment should be used to determine the relationship, considering all relevant factors, including pattern of reaction, temporal relationship, de-challenge or re-challenge, confounding factors such as concomitant medication, concomitant diseases and relevant history.

Arguments that may suggest that there is a reasonable possibility of a causal relationship could be:

- The event is consistent with the known pharmacology of the drug
- The event is known to be caused by or attributed to the drug class.
- A plausible time to onset of the event relative to the time of drug exposure.
- Evidence that the event is reproducible when the drug is re-introduced
- No medically sound alternative etiologies that could explain the event (e.g., preexisting or concomitant diseases, or co-medications).
- The event is typically drug-related and infrequent in the general population not exposed to drugs (e.g. Stevens-Johnson syndrome).
- An indication of dose-response (i.e., greater effect size if the dose is increased, smaller effect size if dose is diminished).

Arguments that may suggest that there is no reasonable possibility of a causal relationship could be:

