7.3.4 Safety analyses

AEs will be coded using the Medical Dictionary for Regulatory Activities (MedDRA) coding dictionary. Standard AbbVie summary tables and listings will be produced. All AEs with an onset between start of treatment and end of the REP, a period of 15 weeks after the last dose of trial medication, will be assigned to the treatment period for evaluation.

All treated patients will be included in the safety analysis. In general, safety analyses will be descriptive in nature and will be based on AbbVie standards. No hypothesis testing is planned.

Statistical analysis and reporting of AEs will concentrate on treatment-emergent AEs. To this end, all AEs occurring between start of treatment and end of the REP will be considered 'treatment-emergent'. The residual effect period is defined as 15 weeks after the last trial medication application. Adverse events that start before first drug intake and deteriorate under treatment will also be considered as 'treatment-emergent'.

Frequency, severity, and causal relationship of AEs will be tabulated by system organ class and preferred term after coding according to the current version of the MedDRA.

Laboratory data will be analysed both quantitatively as well as qualitatively. The latter will be done via comparison of laboratory data to their reference ranges. Values outside the reference range as well as values defined as clinically relevant will be highlighted in the listings. Treatment groups will be compared descriptively with regard to distribution parameters as well as with regard to frequency and percentage of patients with abnormal values or clinically relevant abnormal values.

Vital signs, physical examinations, or other safety-relevant data observed at screening, baseline, during the course of the trial and at the end-of-trial evaluation will be assessed with regard to possible changes compared to findings before start of treatment.

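### SAP Table 11 omits 20 of the 52 routine laboratory tests in the protocol, including all coagulation and quantitative urine tests, with no reason given and no specific output planned for them

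*SAP*

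**What the plan says.** Protocol 5.3.3 states: "The laboratory tests listed in Table 5.3.3: 1 will be performed by the central laboratory service provider". That table includes a coagulation category ("Activated Partial Thromboplastin Time (aPTT) Prothrombin time (INR) Fibrinogen"), a quantitative urine category ("Albumin (quantitative) Creatinine Albumin/creatinine ratio") and a nine-item dipstick ("Urine Nitrite Urine Protein Urine Glucose Urine Ketone Urobilinogen Urine Bilirubin Urine RBC/Erythrocytes Urine WBC/Leukocytes Urine pH"). It marks some tests as screening-only and others as conditional on an abnormal result. The coagulation, dipstick and quantitative urine categories carry neither restriction. The flow chart schedules safety laboratory tests at seven visits: V1, V2, V4, V6, V8, EOT and FU2.

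On analysis, Protocol 7.3.4 states: "Laboratory data will be analysed both quantitatively as well as qualitatively". It explains the qualitative part as comparison with reference ranges and does not limit it to certain tests.

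SAP 11.3.1 is the section on variables and abnormality criteria. Its lead-in to Table 11 is "Clinical laboratory tests performed by central laboratory service provider are listed below", so it claims the same scope as the protocol table. It has no coagulation category and no quantitative urine category, and urine glucose is its only dipstick item.

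SAP 11.3.2 then plans change-from-baseline summaries, shift tables for haematology and clinical chemistry parameters, abnormality criteria and grades (Tables 12 to 14), and separate liver outputs based on ALT, AST, alkaline phosphatase and total bilirubin. SAP 14.1, the place for differences between protocol and SAP, shows a heading with no text beneath it.

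**The concern.** Two lists that claim to be the same thing are not. An analyst who programs from Table 11 and the specific outputs in 11.3.2 would produce no summary by arm for coagulation or quantitative urine tests, although the protocol collects them repeatedly and commits to analysing laboratory data.

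The protocol keeps drug-induced liver injury under surveillance (section 2.3). In section 5.3.6.1 it names coagulopathy among the clinical symptoms of hepatic injury: "icterus, unexplained encephalopathy, unexplained coagulopathy, right upper quadrant abdominal pain, etc". INR and the other coagulation tests bear on that question as supportive data, and the urine albumin/creatinine ratio does the same for renal safety.

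A modest shift in one arm can leave every single value unremarkable, so it shows up in a summary by arm more readily than in case-by-case review. Placebo patients switch to active drug at Week 16, so the comparison with placebo is available only in Part A. There the SAP laboratory windows give two post-baseline time points, Weeks 8 and 16.

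**Working it through.** **Inputs.** Protocol Table 5.3.3: 1 and SAP Table 11, compared item by item. Relative and absolute counts of one cell type count as one test. Pregnancy tests, infection screening and the screening-only hormone and autoantibody tests are left out. The documents give no total of their own to reproduce.

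**Routine tests (not conditional on another result).**

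| Category | Protocol | SAP Table 11 | Omitted |
|---|---|---|---|
| Haematology | 7 | 5 | 2 (RBC, reticulocytes) |
| Automatic differential | 5 | 3 | 2 (basophils, monocytes) |
| Coagulation | 3 | 0 | 3 (aPTT, INR, fibrinogen) |
| Enzymes | 8 | 8 | 0 |
| Electrolytes | 5 | 3 | 2 (chloride, bicarbonate) |
| Substrates | 12 | 12 | 0 |
| Dipstick | 9 | 1 | 8 (all but glucose) |
| Quantitative urine | 3 | 0 | 3 (albumin, creatinine, ratio) |
| **Total** | **52** | **32** | **20** |

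Omitted share: 20 / 52 = 38%. All 32 SAP tests are in the protocol table, so the SAP list is a strict subset.

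**Reflex tests.** CK-MB (1), direct bilirubin, indirect bilirubin and troponin (3), manual differential (6) and urine sediment (6): 1 + 3 + 6 + 6 = 16, none of them in SAP Table 11. With these, the protocol has 52 + 16 = 68 tests and the SAP omits 20 + 16 = 36, or 53%.

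**Do other parts of SAP 11.3 fill the gap?**

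- Shift tables are specified for haematology and clinical chemistry. The protocol classes coagulation and urine separately.
- Tables 12, 13 and 14 contain no coagulation or urine parameter.
- The liver categories, shift tables, by-subject listing and Hy's Law listing use ALT, AST, alkaline phosphatase and total bilirubin only.
- The opening of 11.3 promises listings and descriptive statistics of laboratory values in general terms. It neither names the omitted tests nor excludes them.

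**Tests that define hepatic injury.** Protocol 5.3.6.1 uses ALT, AST and total bilirubin. Omitted from SAP Table 11: 0 of 3.

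**The case against.** The strongest reply is that Table 11 describes tests performed and does not say that others are excluded. No sentence in 11.3.2 ties its outputs to Table 11, and the general promise at the start of 11.3 could cover every test. SAP Section 17, the index of tables and listings, is not in the available text, and Protocol 7.3.4 relies on company reporting standards that are not reproduced. A reader might infer that the omitted tests would never be analysed. The documents do not establish that. They show only that no specific analysis is set out.

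A reader might also infer that the assessment of liver injury is compromised. It is not. All the defining tests are kept and analysed in detail with a Hy's Law listing, and the hepatic adverse-event search in SAP Table 10 includes liver-related coagulation and bleeding disturbances. In the protocol, coagulopathy is a symptom that prompts testing of ALT, AST and total bilirubin; INR is not a criterion.

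Nor would an abnormal result surface only through an investigator's adverse-event report. Under Protocol 5.3.3 the sponsor sees results in real time and selected alerts are flagged, and the data monitoring committee reviews unblinded safety data (3.1.2). These routes address safety during the trial. They do not supply the summary by arm that the protocol's analysis section leads one to expect.

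Finally, the percentage gives urine pH the same weight as INR, and 8 of the 20 omitted routine tests are dipstick items. That is fair. The two categories that are missing entirely matter more than the total.

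**Conclusion.** The point stands as an unexplained mismatch between protocol and SAP in safety reporting. SAP Table 11 omits 20 of 52 routine tests (36 of 68 with all reflex items), including the whole of the coagulation and quantitative urine categories. The available SAP text specifies no table or listing for them. Supportive liver, coagulation and renal data are affected; the core hepatic-injury analysis and the efficacy endpoints are not. It should be corrected, because the protocol's commitment is general and the remedy is cheap.

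The conclusion rests on three assumptions: that routine tests without a restriction in the protocol table are run at each scheduled safety laboratory visit; that the counting rules above are accepted; and that the unavailable parts of the SAP, Section 17 in particular, do not already provide for these tests. If Section 17 does, what remains is to correct Table 11.

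**What to change.** - Reconcile SAP Table 11 with Protocol Table 5.3.3: 1, stating for each test whether it is summarised, listed or left out.
- Add aPTT, INR, fibrinogen and the urine albumin/creatinine ratio to the change-from-baseline summaries and reference-range shift tables for Part A and Part B. Extending these to ALL_RZB is unnecessary, because for laboratory data the SAP plans only the table of potentially clinically important values there.
- Show INR alongside the existing parameters in the by-subject liver listing.
- Present direct and indirect bilirubin, CK-MB and troponin as listings only. They are measured only when another result triggers them, so many patients would have no baseline value and any summary would cover a subset selected after randomisation.
- Record in SAP 14.1 every protocol test deliberately left out, with the reason.

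The cost is SAP wording and further runs of existing laboratory programs on data the protocol already collects; no new samples are needed. The drawback is a longer laboratory output with more unadjusted comparisons, which should be read descriptively.

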11.3.2 Statistical Methods

All analyses will be conducted in the Safety Population. Table for potentially clinically important lab values will also be summarized in the ALL_RZB Population.

Analysis of Continuous Laboratory Parameters

Though the protocol indicates utilizing the Rheumatology Common Toxicity Criteria (RCTC) scale for grading laboratory values, given that the NCI National Cancer Institute Common Toxicity Criteria for Adverse Event (CTCAE) scale includes a more comprehensive list of laboratory values; therefore, the lab analyses based on the NCI CTCAE scale will be presented. Change from Baseline to each scheduled visit and to the final value in continuous laboratory parameters will be summarized with the mean, standard deviation and median. The Baseline and visit/final value means will also be presented for subjects who have both the Baseline and visit/final values (see Section 6.0 for the definition of Baseline and final values). If there are multiple post-baseline measurements on the same day, the average value will be used.

Shift Tables

Shift tables for changes from Baseline according to the normal range will be provided for each hematology and clinical chemistry parameter. Shifts from Baseline to the following endpoints will be considered: minimum value, maximum value and final value. Categories of "low or normal" and "high or normal" will be included at Baseline in addition to the categories of "low," "normal," "high" and "missing." If there are multiple measurements on the same day, the last value will be used.

Potentially Clinically Important Laboratory Values

Frequencies and percentages of subjects with post Baseline lab values meeting the following criteria will be summarized. Of note, a post baseline value must be more extreme than the baseline value to be considered a potentially clinically important finding.

Table 12. Criteria for Potentially Clinically Important Chemistry Values

Chemistry Variables	Units	Definition of Potentially Clinically Important Current (Version 4) NCI CTCAE Grade 3 or Greater	
		Very Low	Very High
TBL	mcmol/L		> 3.0 × ULN
SGOT/AST	U/L		> 5.0 × ULN
SGPT/ALT	U/L		> 5.0 × ULN
Albumin	g/L	< 20	
Glucose	mmol/L	< 2.2	> 13.9
Triglycerides	mmol/L		> 5.7
Creatinine	mcmol/L		> 3.0 × ULN
Sodium	mmol/L	< 130	> 155
Potassium	mmol/L	< 3.0	> 6.0
Calcium	mmol/L	< 1.75	> 3.1
CPK	U/L		> 5.0 × ULN
Total Cholesterol	mmol/L		> 10.34
GGT			> 5.0 × ULN
ALP			> 5.0 × ULN
Lipase			> 5.0 × ULN
Amylase			> 5.0 × ULN

Table 13. Criteria for Potentially Clinically Important Hematology Values

Hematology Variables	Units	Definition of Potentially Clinically Important Current (Version 4) Grade 3 or Greater	
		Very Low	
Hemoglobin	g/dL	< 8.0	
Platelets count	10 ⁹ /L	< 50.0	
WBC count	10 ⁹ /L	< 2.0	
Neutrophils	10 ⁹ /L	< 1.0	
Lymphocytes	10 ⁹ /L	< 0.5	

A separate listing will be provided that presents all of the subjects and values that are NCI CTCAE toxicity grade 3 or above. For each of these subjects, the whole course of the

respective parameter will be listed. The NCI CTCAE grading is shown in [Table 14](#) below:

Table 14. NCI CTCAE Grading

Test	Grade 1	Grade 2	Grade 3	Grade 4
SGPT/ALT increased	$> \text{ULN} - 3.0 \times \text{ULN}$	$> 3.0 - 5.0 \times \text{ULN}$	$> 5.0 - 20.0 \times \text{ULN}$	$> 20.0 \times \text{ULN}$
SGOT/AST increased	$> \text{ULN} - 3.0 \times \text{ULN}$	$> 3.0 - 5.0 \times \text{ULN}$	$> 5.0 - 20.0 \times \text{ULN}$	$> 20.0 \times \text{ULN}$
GGT increased	$> \text{ULN} - 2.5 \times \text{ULN}$	$> 2.5 - 5.0 \times \text{ULN}$	$> 5.0 - 20.0 \times \text{ULN}$	$> 20.0 \times \text{ULN}$
ALP increased	$> \text{ULN} - 3.0 \times \text{ULN}$	$> 3.0 - 5.0 \times \text{ULN}$	$> 5.0 - 20.0 \times \text{ULN}$	$> 20.0 \times \text{ULN}$
TBL increased	$> \text{ULN} - 1.5 \times \text{ULN}$	$> 1.5 - 3.0 \times \text{ULN}$	$> 3.0 - 10.0 \times \text{ULN}$	$> 10.0 \times \text{ULN}$
Creatinine increased	$> \text{ULN} - 1.5 \times \text{ULN}$	$> 1.5 - 3.0 \times \text{ULN}$	$> 3.0 - 6.0 \times \text{ULN}$	$> 6.0 \times \text{ULN}$
CPK increased	$> \text{ULN} - 2.5 \times \text{ULN}$	$> 2.5 - 5.0 \times \text{ULN}$	$> 5.0 - 10.0 \times \text{ULN}$	$> 10.0 \times \text{ULN}$
Hemoglobin decreased	$< \text{LLN} - 100.0 \text{ g/L}$	$< 100.0 - 80.0 \text{ g/L}$	< 80.0	
Neutrophil count decreased	$< \text{LLN} - 1.5 \times 10^9/\text{L}$	$< 1.5 - 1.0 \times 10^9/\text{L}$	$< 1.0 - 0.5 \times 10^9/\text{L}$	$< 0.5 \times 10^9/\text{L}$
WBC decreased	$< \text{LLN} - 3.0 \times 10^9/\text{L}$	$< 3.0 - 2.0 \times 10^9/\text{L}$	$< 2.0 - 1.0 \times 10^9/\text{L}$	$< 1.0 \times 10^9/\text{L}$
Lymphocyte count decreased	$< \text{LLN} - 0.8 \times 10^9/\text{L}$	$< 0.8 - 0.5 \times 10^9/\text{L}$	$< 0.5 - 0.2 \times 10^9/\text{L}$	$< 0.2 \times 10^9/\text{L}$

If there are multiple post-baseline measurements on the same day, the worst value will be used.

Liver Function Tests

Additional summaries will be presented for liver function tests including ALT or serum glutamic-pyruvic transaminase (SGPT), AST or serum glutamic-oxaloacetic transaminase (SGOT), alkaline phosphatase, and total bilirubin. Each laboratory value will be categorized as follows:

- $< 1.5 \times \text{ULN}$
- $\geq 1.5 \times \text{ULN} - < 3.0 \times \text{ULN}$

- $\geq 3.0 \times \text{ULN} - < 5.0 \times \text{ULN}$
- $\geq 5.0 \times \text{ULN} - < 10.0 \times \text{ULN}$
- $\geq 10.0 \times \text{ULN} - < 20.0 \times \text{ULN}$
- $\geq 20.0 \times \text{ULN}$

Shift tables of Baseline to the maximum (relative to the normal range, i.e., the largest multiple relative to the upper limit of normal) values, and from Baseline to final value will be presented using these categories. A listing of potentially clinically important liver function laboratory values will be provided. The listing will include all subjects who met any of the following four criteria:

- $\text{ALT} \geq 3 \times \text{ULN}$, or
- $\text{AST} \geq 3 \times \text{ULN}$, or
- Alkaline phosphatase $\geq 1.5 \times \text{ULN}$, or
- Total bilirubin $\geq 2 \times \text{ULN}$.

A listing of possible Hy's Law cases, defined as those who meet all of the following conditions will be provided:

- $\text{ALT} > 3 \times \text{ULN}$ or $\text{AST} > 3 \times \text{ULN}$
- Associated with an increase in bilirubin $\geq 2 \times \text{ULN}$
- Alkaline phosphatase $< 2 \times \text{ULN}$.

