- Determine the window around a specific nominal Rx day by adding or subtracting half of the interval between adjacent visits (e.g., days between Week 4 and Week 8 is 28). The threshold between adjacent visits is determined by splitting the interval evenly between the visits. If the resulting split is between Rx days, then the threshold is determined as the midpoint between the adjacent visits. If the resulting split is on an Rx day, then the threshold is determined as being between that Rx day and the Rx day prior to it (e.g., the split between Week 4 and Week 8 would be between Rx Days 43 and 44).
- If more than one assessment is included in a time window the assessment closest to the nominal day will be used. If there are two observations equidistant to the nominal day, the later one will be used in analyses. If more than one assessment is included on the same day, then the worst assessment on that day will be used in analyses, except those specified in Section 11.0.

The following analysis windows have been specified for the analysis of efficacy, laboratory parameters, and vital signs, etc. for each analysis period. In order to include all post baseline data, the first post baseline interval starts on the day after the date of first study drug injection in each period (Rx Day 2) for all efficacy variables.

For subjects who were randomized and not dosed date of randomization will be used for determining window definitions.

Table 2.
Visit Windows for Analysis of PASI, Vital Signs, and Local Tolerability in Part A (ITT/PP/Safety Populations)

Window Label	Target Day	Interval
Baseline	1	$\leq 1^a$
Week 4	29	[2, 43]
Week 8	57	[44, 71]
Week 12	85	[72, 99]
Week 16	113	[100, 127 ^b]

Rx Day calculated relative to first dose date of study drug. For subjects randomized but not dosed, Rx Day calculated relative to Randomization.

- a. There is no baseline for local tolerability measurements. If time is collected in vital signs, restrict to records prior to the first dose of study drug.
- b. The minimum of upper bound and the day of the first dose date in Part B (and within 105 days of last dose for safety analyses).

Table 3.
Visit Windows for Analysis of Safety Laboratory Tests in Part A (Safety Population)

Window Label	Target Day	Interval
Baseline	1	≤ 1
Week 8	57	[2, 85]
Week 16	113	[86, 141*]

Rx Day calculated relative to first dose date of study drug.

* The minimum of upper bound, the day of the first dose date in Part B, and 105 days of last dose.

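### The laboratory shift tables apply a last-reading-of-the-day rule to the minimum and maximum, so a less extreme same-day repeat can hide the true extreme

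*SAP*

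**What the plan says.** SAP 11.3.2 gives a separate same-day rule to each of three laboratory outputs.

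- **Continuous summaries (change from Baseline):** "If there are multiple post-baseline measurements on the same day, the average value will be used".
- **Shift tables:** these are based on the normal range: "Shift tables for changes from Baseline according to the normal range will be provided for each hematology and clinical chemistry parameter". The endpoints are then named: "Shifts from Baseline to the following endpoints will be considered: minimum value, maximum value and final value". The paragraph ends with "If there are multiple measurements on the same day, the last value will be used". There is no exception for the minimum or maximum, and nothing says that they are found before the same-day rule is applied. Unlike the other two rules, this one is not limited to post-baseline readings.
- **Potentially clinically important values and the Grade 3+ listing:** "Frequencies and percentages of subjects with post Baseline lab values meeting the following criteria will be summarized", using the limits in Tables 12 and 13. After Table 14 comes "If there are multiple post-baseline measurements on the same day, the worst value will be used". I read that sentence as covering both the counts and the listing.

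Three other places bear on the point. SAP 6.0 (analysis windows) sets a general default with room for exceptions: "then the worst assessment on that day will be used in analyses, except those specified in Section 11.0". SAP 11.3 promises a summary of extreme abnormal values and defines the term: "Extreme abnormal value is the value which is most significantly away from the reference range". The liver function shift tables, later in 11.3.2, use each patient's largest multiple of ULN and state no same-day rule.

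**The concern.** A last-of-day rule chooses one reading to stand for a day. That is sensible when the endpoint is itself a last reading, and SAP 6.0 defines both Baseline and the final observation as a last non-missing observation. A minimum or maximum is a different kind of endpoint, because it is meant to catch the most extreme reading. Filtering each day to its last reading first can remove the value that the table is meant to show.

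Two things are at stake. A shift to low or high can go unreported. And two safety tables built from the same laboratory data can describe one patient differently, with a Grade 3 or greater value in one and a normal maximum or minimum in the other. Protocol 5.3.3 makes the loss more likely where a repeat does fall on the same day: clinically relevant abnormal results must be confirmed and then repeated until they normalise or stabilise, so later readings will tend to be the milder ones.

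**Working it through.** The plan states no figure to reproduce here. The check applies the SAP's own rules to assumed readings.

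**1. Direction, post-baseline side.** Let S be all of a patient's post-baseline readings of one test, and L the subset left after keeping only the last reading of each day. Because L is contained in S:

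- max(L) ≤ max(S)
- min(L) ≥ min(S)

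A shift to high is lost when max(S) is above the upper normal limit and max(L) is not. A shift to low is lost in the mirror case. Neither inequality can reverse, so the filter cannot create a post-baseline shift.

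**2. ALT, high side.** Assumed readings: 6.0 then 0.9 × ULN on one day, and 0.8 × ULN at another visit. Table 12 limit: > 5.0 × ULN.

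| Same-day rule | Value for the day | Maximum over visits | Normal range | Grade 3+ |
|---|---|---|---|---|
| Last (shift tables) | 0.9 | 0.9 | normal | no |
| Worst (important values) | 6.0 | 6.0 | high | yes |
| Average (continuous) | (6.0 + 0.9)/2 = 3.45 | 3.45 | high | no |

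The patient is Grade 3+ in one table and has a normal maximum in the shift table.

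**3. Potassium, high side.** Assumed readings: 6.2 then 4.4 mmol/L on one day, with no other reading above 4.4. The worst value, 6.2, exceeds the Table 12 limit of 6.0 and is counted as very high. The shift to maximum records 4.4.

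**4. Neutrophils, low side.** Assumed readings: 0.9 then 2.5 × 10⁹/L on one day, and 3.0 at another visit. The last-value rule gives a minimum of 2.5. The worst-value rule gives 0.9, below the Table 13 limit of 1.0. The documents do not give the laboratory's normal limits, so whether 2.5 would be shown as normal is an assumption. The understated minimum does not depend on it.

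**5. Reverse order.** ALT of 0.9 then 6.0 × ULN gives 6.0 under both the last and the worst rule, and nothing is lost. The same holds if another day also reaches 6.0.

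So the true extreme is lost only if (a) there are two or more readings on the day of the extreme, (b) the last of them is less extreme, and (c) no other day is as extreme. A changed category also needs the retained value to fall in a different normal-range class.

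**6. Scale, under assumption.** The documents give no rate of same-day repeats. Suppose a share s of the 168 planned patients has a same-day repeat on the day of their extreme for a given test. The expected number with a lost extreme is 168 × s × P(last reading less extreme).

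| s (assumed) | P = 0.5 (random order) | P = 1 (later reading always milder) |
|---|---|---|
| 0.5% | 168 × 0.005 × 0.5 = 0.42 | 0.84 |
| 5% | 168 × 0.05 × 0.5 = 4.2 | 8.4 |

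The number with a changed category would be no larger than these.

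**The case against.** The strongest reply is that this is a permitted choice. SAP 6.0 makes worst-of-day the default but allows exceptions in Section 11, and 11.3.2 gives three outputs three rules. That stands: a reader might infer a breach of SAP 6.0, and there is none. It does not remove the mismatch between a last-of-day filter and an endpoint called a minimum or maximum.

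The second reply is that same-day pairs will be rare. The protocol flow chart schedules no paired safety laboratory samples within a visit. Protocol 5.3.3 calls for confirmation with an unscheduled-visit kit, and 6.1 allows additional visits for re-testing. Neither says that the repeat is taken on the same day, and a repeat on a later day is untouched by the rule. A reader might also picture a same-day check at a local laboratory. The protocol allows local testing only exceptionally, SAP 11.3.1 lists tests done by the central laboratory, and nothing shows local results entering these tables. All of this stands and limits the size.

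Third, most of the safety information survives elsewhere. Grade 3+ counts use the worst value, the whole course of the parameter is listed for those patients, and 11.3 promises extreme abnormal values. That also stands. The main loss is a milder excursion that normalised on the same day, plus the possible disagreement between tables.

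Finally, a reader might infer that every case biases the tables the same way. That holds only after Baseline. As worded, the rule covers Baseline too. A high Baseline reading repeated as normal that day is classed as normal, so a later high value counts as a new shift that would not count if the first reading had been kept.

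**Conclusion.** The point holds as a minor one. The shift-table rule, followed literally, can return a minimum or maximum that is not the patient's extreme. On the post-baseline side the error can only lose shifts. The result can contradict the Grade 3+ count for the same patient, but it need not: the three conditions in the check must all hold, and a visible contradiction also needs the retained value to lie within the normal range.

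It would be too strong to say that any same-day repeat erases the extreme, or that the number of patients affected equals the number of repeats. That number is an upper bound, since a repeat that confirms or exceeds the earlier reading changes nothing. The documents do not give it, and the figures of about 0.4 to 8.4 patients per test rest entirely on the assumed 0.5% to 5%. The real number is probably small. Only descriptive safety tables are affected; efficacy and alpha are not.

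**What to change.** Replace the same-day sentence under Shift Tables in SAP 11.3.2 with wording such as: the minimum and maximum are taken over all post-baseline readings in the analysis period; where Baseline or the final value falls on a day with several readings, the last reading of that day is used. Keeping Baseline in the sentence matters, because a rule for the minimum, maximum and final value alone would leave the shift tables with no stated same-day rule for Baseline.

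State the same rule for the liver function shift tables. At present their silence leaves a programmer to choose between the worst-of-day default in SAP 6.0 and the last-of-day rule of the other shift tables.

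The cost is one sentence, a cross-reference and a small programming change. The only visible consequence is that a few more patients may be shown as shifted.
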